## 10.2. Overdose

An overdose is defined as administering at least 25% more than the protocol-specified dose (i.e.,  $\geq 125\%$  of the protocol-specified dose). Overdoses should be reported to the Coordinating Center regardless of occurrence of adverse event within 24 business hours of discovery as instructed per section 11.6. The clinical manifestation (if any) of an overdose should be reported as an AE or SAE, as appropriate.

### 10.2.1. Pregnancy

During the course of the trial, all female patients of childbearing potential (the definition of “women of childbearing potential” is listed in Appendix D), must contact the treating investigator immediately if they suspect that they may be pregnant (a missed or late menstrual period should be reported to the treating investigator) after the first dose of study treatment until end-of-treatment procedures are performed.

Male patients that suspect they may have impregnated a partner must also notify the treating investigator immediately. If an investigator suspects that a patient may be pregnant prior to administration of trial drug(s), the trial drug(s) must be withheld until the result of the pregnancy test is confirmed.

If a pregnancy is confirmed, the patient must not receive any trial drug(s), and must be discontinued from the trial, and the investigator must notify the Coordinating Center as soon as possible. The Coordinating Center will report the pregnancy to a Sunesis representative.

Subjects and their partners with reproductive potential must agree to use effective contraceptive measures during the study and for 2 months after the last dose of study treatment.

See Appendix D for information regarding effective contraception measures.

## 11. ADVERSE EVENT DEFINITIONS AND REPORTING

### 11.1. Adverse Event Definitions According to ICH Guidelines and FDA Final Rule on Safety Reporting Requirements

Updated definitions according to both ICH and the FDA final rule are provided within Table 4.

**Table 4. Adverse Event Definitions**

Term	Definitions per FDA Final Rule
Adverse Event	Any untoward medical occurrence associated with the use of a drug in humans, whether or not considered drug related
Suspected adverse reaction	Any adverse event for which there is a reasonable possibility that the drug caused the adverse event. For the purposes of IND safety reporting, “reasonable possibility” means there is evidence to suggest a causal relationship between the drug and the adverse event.  Suspected adverse reaction implies a lesser degree of certainty about causality than adverse reaction, which means any adverse event caused by a drug.
Unexpected adverse event or unexpected suspected adverse reaction	An adverse event or suspected adverse reaction is considered “unexpected” if it is not listed in the investigator brochure or is not listed at the specificity or severity that has been observed.  Includes adverse events or suspected adverse reactions that are mentioned in the investigator brochure as occurring with a class of drugs or as anticipated from the pharmacological properties of the drug, but are not specifically mentioned as occurring with the particular drug under investigation.

Term	Definitions per FDA Final Rule
Serious adverse event or serious suspected adverse reaction	
Any untoward medical occurrence that at any dose, in the opinion of the investigator or sponsor:
 
 
• Results in death, Is life-threatening, NOTE: The term “life-threatening” in the definition of “serious” refers to an event in which the patient was at risk of death at the time of the event; it does not refer to an event which hypothetically might have caused death if it were more severe.
 
• Results in a persistent or significant incapacity or a substantial disruption of the ability to conduct normal life functions,
 
• Is a congenital anomaly/birth defect.
 
• Important medical events that may not result in death, be life-threatening, or require hospitalization may be considered serious when, based upon appropriate medical judgment, they may jeopardize the patient or subject and may require medical or surgical intervention to prevent one of the outcomes listed in this definition.
 

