placebo/cytarabine). In a predefined analysis censoring for subsequent ASCT, median OS was improved with vosaroxin+cytarabine (6.7 mo vs 5.3 mo with placebo+cytarabine; HR = 0.81 [95% CI: 0.67-0.97];  $P = 0.02$ ; stratified  $P = 0.03$ ). In predefined subgroup analyses, OS benefit was greatest in patients aged  $\geq 60$  years (7.1 mo with vosaroxin+cytarabine vs 5.0 mo with placebo+cytarabine; HR = 0.75;  $P = 0.003$ ) and those with early relapse (6.7 mo vs 5.2 mo; HR = 0.77;  $P = 0.04$ ). OS with vosaroxin+cytarabine vs. placebo+cytarabine was 9.1 mo vs 7.9 mo in patients  $< 60$  years (HR = 1.08;  $P = 0.60$ ); 6.7 mo vs 5.0 mo in patients with refractory disease (HR = 0.87;  $P = 0.23$ ); and 14.1 mo vs 12.3 mo in patients with late relapse (HR = 0.98;  $P = 0.96$ ), respectively. A CR was achieved in 30.1% of patients treated with vosaroxin+cytarabine vs. 16.3% treated with placebo+cytarabine ( $P = 0.00001$ ).

Thirty-day and 60-day all-cause mortality was similar in the 2 arms (30-day: 7.9% vs 6.6%; 60-day: 19.7% vs 19.4% with vosaroxin+cytarabine vs. placebo+cytarabine, respectively). Most common serious AEs were febrile neutropenia (11.3% with vosaroxin+cytarabine vs. 7.4% with placebo/cytarabine), sepsis (8.7% vs 4.3%), pneumonia (7.6% vs 4.9%), bacteremia (8.5% vs 2.9%), and stomatitis (3.4% vs 1.4%). Serious and non-serious cardiac, renal, neurologic, and hepatic AEs were comparable between treatment groups.

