### 11.7. Serious Adverse Event Reporting Requirements

Study site personnel must report all SAEs by fax as soon as possible to the Coordinating Center, but within 1 business day of first becoming aware of the SAE. The following minimum information is required by the sponsor:

- Patient identification (i.e., study number, sex, age)
- Description of the SAE (diagnosis preferred, symptoms, etc.)
- Investigator name
- Study drug and causal relationship of the SAE to the study drug(s)

The SAE report should be submitted via secure email transfer or via fax using the contact information listed below:

Attn: VICC Multi-Institutional Coordinating Center

[contact]

or

[contact]

Transmission of the SAE report should be confirmed by the site personnel submitting the report.

Follow-up information for SAEs and information on non-serious AEs that become serious should also be reported to the Coordinating Center as soon as it is available; these reports should be submitted using the SAE Report Form.

Investigators must submit written safety reports as required by their Institutional Review Board (IRB) or Institutional Ethics Committee (IEC) within timelines set by regional regulations (European Union common technical document or US FDA). The study site should retain documentation of the submission of expedited safety reports to the IRB/IEC, and their receipt.

Persistent or recurrent AML (or “disease progression”), including AML leading to death, should not be recorded as an SAE. Persistent or recurrent AML is an outcome of treatment and will be documented as treatment failure. Associated events resulting from persistent or recurrent AML (or “disease progression”) should be recorded as AE or SAEs, and SAEs resulting in death should be documented.

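### Table 4 leaves hospitalization off its list of serious criteria, although its last bullet treats hospitalization as one of them

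*Combined protocol and SAP*

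**What the plan says.** Section 11.1 introduces the definitions as authoritative: "Updated definitions according to both ICH and the FDA final rule are provided within Table 4". The SAE row of Table 4 then gives:

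- death and threat to life, run together in one entry: "Results in death, Is life-threatening, NOTE";
- incapacity: "Results in a persistent or significant incapacity or a substantial disruption of the ability to conduct normal life functions";
- congenital anomaly: "Is a congenital anomaly/birth defect";
- a judgement criterion that starts "Important medical events that may not result in death, be life-threatening, or require hospitalization may be considered serious" and applies where the event may jeopardize the patient and may need intervention "to prevent one of the outcomes listed in this definition".

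Section 11.7 attaches the reporting duty to SAE status: "Study site personnel must report all SAEs by fax as soon as possible", with a limit of 1 business day from first awareness. Section 11.8 has the sponsor pass every SAE to the drug supplier, whatever its cause.

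**The concern.** The last bullet sets hospitalization beside death and threat to life, as a serious outcome that an important medical event happens to lack. Death and threat to life are on the list and hospitalization is not, so the definition disagrees with itself. No text says that hospitalization was left out on purpose, for instance because induction is given to inpatients.

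What is at stake is whether an admission alone makes an event serious. A site that works from the list would answer no. A site that works from the sense of the last bullet would answer yes. The trial enrols at several institutions through a Coordinating Center (section 5.1.1), so similar readmissions could be reported within a day at one site and not at all as SAEs at another.

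**Working it through.** No arithmetic applies. The check compares the list with the bullet that refers to it, and then looks for a repair elsewhere.

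**Step 1: count the criteria.** The SAE row has four outcome criteria and one judgement criterion.

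| Outcome | Listed as a criterion in Table 4 | Named in the last bullet |
|---|---|---|
| Death | yes | yes |
| Threat to life | yes | yes |
| Incapacity | yes | no |
| Congenital anomaly | yes | no |
| Hospitalization | no | yes |

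Hospitalization occurs once in the SAE definition, and only in the bullet that presupposes it.

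**Step 2: look for the criterion elsewhere.** Sections 11.3 to 11.8 use the terms SAE and seriousness without redefining them. Section 12.6 does not mention either. Appendix E refers to treatment of neutropenic fever in hospital, but as care and not as a reporting criterion. Nothing supplies the missing item.

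**Step 3: apply the rules literally to a patient who is admitted.**

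| Event | SAE under Table 4? | Recorded under section 11.3? |
|---|---|---|
| Fatal or life-threatening | yes, whatever the admission | yes |
| Grade 3 or higher, no listed outcome, admitted | only by judgement | yes, with a seriousness field |
| Grade 1 or 2, of special interest (mucositis, infection, neutropenia, diarrhea, thrombocytopenia), admitted | only by judgement | yes |
| Grade 1 or 2, any other kind, admitted | only by judgement | not required |

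In the last three rows the 1-business-day report and the supplier report follow only if the judgement is made. The seriousness field in section 11.3 does not close the gap, because whoever completes it uses the same Table 4.

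**Step 4: check what the planned analysis uses.** Section 12.6 summarises adverse events by grade, attribution, organ class and preferred term. Seriousness is not among these, so reclassifying an event as serious or non-serious changes no planned safety summary.

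**Step 5: size.** It would require the number of events that are serious through hospitalization alone. The documents give no hospitalization rate for this or any cited trial, so no figure follows.

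**The case against.** The best case for leaving this alone is that little is lost. The common toxicities are recorded under section 11.3 whether or not they are called serious. The cancer center's data and safety monitoring committee reviews all reported adverse events, not only SAEs (section 13.1.5). Section 13.1 requires compliance with federal regulations and ICH guidelines and applies the strictest standard where requirements differ. Table 4 lets the sponsor as well as the investigator call an event serious. An investigator could also treat an admission as a disruption of normal life under the incapacity criterion. Finally, the first entry of the list runs two criteria together, so a line lost from the table cannot be wholly excluded.

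Much of this stands, and it limits the consequence. It does not repair the definition. The strictest-standard clause settles conflicts between local, FDA and ICH requirements, not between Table 4 and its own last bullet. The other routes depend on judgement, and the sponsor can normally exercise its own only on events that reach it. No gap is visible in the table, and checking the formatted page takes minutes.

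A reader might also infer four stronger things, none of which the documents support:

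- **That about 5 of 41 patients are affected.** The cited phase 3 trial reports serious febrile neutropenia in 11.3%, and 0.113 × 41 = 4.6. This assumes that every such event was serious only through hospitalization, and the documents give no breakdown by criterion. The trial also enrolled relapsed or refractory patients, whereas this one enrols untreated patients.
- **That SAE counts cannot be compared with the cited trials.** The SAE definitions of those trials are not given, and no such comparison is planned.
- **That reports to the FDA would be lost.** Section 11.8 requires an event to be unexpected as well as serious. Section 10.1.1 cites the investigator brochure for febrile neutropenia (36.9%) and infections (39.7%) in hematologic malignancies, so ordinary readmissions for these would generally be expected.
- **That the safety objective is compromised.** The planned safety summaries do not use seriousness.

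**Conclusion.** The inconsistency is real and lies within Table 4 itself, so it needs no outside source to establish. Followed literally, the definition leaves events that are serious only through hospitalization outside mandatory SAE reporting unless someone judges them medically important. Classification, the 1-business-day report and the supplier report can then be missed or vary by site. Such variation is possible, not certain, since sites may apply the definition they know from other trials.

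The effect stops at SAE classification and expedited reporting. The primary endpoint and the planned safety summaries by grade and term do not depend on it, apart from lower-grade events outside the special-interest list, which might go unrecorded. Its size cannot be derived from the documents. The conclusion assumes that the table is complete as it reads.

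**What to change.** Reconcile Table 4 with its last bullet. Add inpatient hospitalization, or prolongation of an existing hospitalization, as a serious criterion, and state how the planned induction stay is handled so that the stay does not itself generate SAEs. If hospitalization was left out on purpose, say so, give the reason, and reword the last bullet so that it no longer presents hospitalization as one of the serious outcomes.

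The cost is one line in the table and a sentence on the induction stay. If the criterion is added, sites will complete some additional SAE forms. Sample size and the planned analyses are unaffected.

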### 11.2. Eliciting Adverse Event Reports

Simple, unbiased questions should be asked to elicit reports of AEs during the clinical study. For example:

- How have you felt since your last visit?
- Have you had any health problems since you were last here?

### 11.3. Assessment and Recording of Adverse Events

All AEs grade 3 or higher occurring during the reporting period must be assessed and recorded as follows:

- Name of the event (diagnosis preferred, otherwise state signs and symptoms)
- Date of onset and stop date (if available)
- Course (i.e., intermittent, ongoing)
- Maximum intensity or severity (grade) based on the NCI CTCAE version 4.03
- Relationship to study treatment
- Seriousness
- Outcome
- Use of concomitant medication to treat a patient for an AE

**Adverse events of special interest that occur at grade 1 or higher will be recorded. Adverse events of special interest are: mucositis, infection, neutropenia, diarrhea, and thrombocytopenia.**

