## 5.2. Treatment / Hematologic Recovery

The treatment period will include up to two cycles of treatment (Induction 1, Induction 2). In each cycle, the first day of study treatment will be considered day 1. Each cycle will include vosaroxin treatment on Days 1 and 4 and cytarabine on Days 1-7 followed by a variable interval required to achieve hematologic recovery defined as absolute neutrophil count (ANC) > 1000 cells/ $\mu$ L and platelets > 100,000 cells/ $\mu$ L. Hematologic recovery is expected to occur approximately 5 to 6 weeks after the first treatment day of each cycle. Each cycle will be a minimum of 14 days and a maximum of 8 weeks.

### 5.2.1. Induction 1

An early assessment of antileukemic activity (bone marrow biopsy or aspirate) will be performed at approximately Day 14 for the sole purpose of guiding treatment decisions. If the early treatment assessment indicates an ablated bone marrow with < 5% blasts, CBC will be examined as noted in the schedule of events thereafter to monitor for hematologic recovery.

If the early treatment assessment indicates residual leukemia ( $\geq$  5% blasts) and a second cycle is indicated in the judgment of the investigator, the investigator may initiate Induction 2 any date prior to Induction 1 day 57 (no later than 8 weeks after Induction 1, Day 1) if eligibility criteria are met. Bone marrow assessments may be repeated as necessary per standard of care (investigator discretion) to clarify or confirm a finding of residual leukemia. In the event that blasts are  $\geq$  5% blasts, but  $\leq$  10%, the investigator may choose to pursue an additional bone marrow biopsy at a future date prior to making decision on whether Induction 2 is warranted.

### 5.2.2 Induction 2

Induction 2 will not be necessary for all patients, but may be appropriate if the Induction 1 early treatment or hematologic recovery assessment indicates residual leukemia is present, and if a second cycle is indicated in the judgment of the investigator. Eligibility for Induction 2 requires that non-hematologic toxicity and abnormal laboratory values be resolved to grade  $\leq$  1, if assessed by the investigator as related to treatment and clinically significant. Recovery of ANC, hemoglobin/hematocrit, and/or platelet counts is not required prior to Induction 2.

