## 10. SAFETY ASSESSMENTS

### 10.1. Safety Monitoring

#### 10.1.1. Common Adverse Events Attributed to Vosaroxin

The safety profile of vosaroxin is consistent with the common pharmacologic effects of cytotoxic chemotherapeutic agents. Myelosuppression (including associated fatal infections) and gastrointestinal (GI) toxicity (including nausea, diarrhea, and upper GI mucositis) are known risks associated with vosaroxin treatment. Oral mucositis (stomatitis) was the DLT in patients with hematologic malignancies treated with higher doses of vosaroxin: up to 40 mg/m^2 once weekly for 4 weeks (28-day cycle) or up to 90 mg/m^2 once weekly for 3 weeks (28 day cycle; up to 270 mg/m^2/cycle). In patients treated with vosaroxin, oral mucositis is dose limiting and grade 3 or 4 oral mucositis usually appears within 2 weeks after the first dose.

Per the most recent reference safety information (IB, Version 12), infections and febrile neutropenia were reported at a higher frequencies in patients with hematologic malignancies (39.7% and 36.9 of 648 patients respectively) than in patients with solid tumors (12.3% and 9.2% of 284 respectively). The GI toxicities of stomatitis and diarrhea were also reported at higher frequencies in patients with hematologic malignancies (46.8% and 47.7% respectively) than in

patients with solid tumors (11.3% and 17.3% respectively). For patients with hematologic malignancies who received vosaroxin (N = 648), the most common treatment-related AEs (with at least 20% incidence) include nausea (53.2%), diarrhea (47.7%), stomatitis (46.8%), febrile neutropenia (36.9%), decreased appetite (31.3%), vomiting (30.1%), anemia (29.0%), thrombocytopenia (28.5%), neutropenia (20.1%), and fatigue (21.0%). The only two grade 3 and 4 treatment-related AEs reported in at least 20% of all vosaroxin treated patients (N = 932) are febrile neutropenia (26.4%) and neutropenia (21.5%).

For patients with AML treated with higher doses of vosaroxin, oral mucositis is dose limiting and grade 3 or 4 oral mucositis usually appears within 2 weeks after the first dose. Oral mucositis can be managed with standard supportive care (Appendix E). The incidence of combined grade 3 and 4 nausea and vomiting in vosaroxin studies is low (2.7% and 1.4% respectively).

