#### **11.5. Intensity of the Adverse Event**

The investigator will grade each reportable AE based on its maximum intensity (or severity) using the NCI CTCAE V4.03 (available at: <http://evs.nci.nih.gov/ftp1/CTCAE/About.html>). If no grading criteria are provided for the AE, it should be graded using the scale presented in Table 5, noting that not all grades are appropriate for all AEs.

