**Table 5. Definition of Adverse Event Attribution**

Attribution	Description
Unrelated	The AE is clearly NOT related to the intervention.
Unlikely:	The AE is doubtfully related to the intervention.
Possible:	The AE may be related to the intervention.
Probable:	The AE is likely related to the intervention.
Definite:	The AE is clearly related to the intervention.

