### 12.6. Safety Analysis

Adverse events and laboratory data will be graded according to the NCI CTCAE version 4.03. As described above frequency and percentage of patients will be summarized for any adverse event by grade, attribution, organ class, and preferred term overall and by patient. Change in continuous laboratory data from just prior to therapy and by visit will be summarized by frequency of abnormal values. Linear and non-linear regression will be used to model changes over time, accounting for intra-patient correlation using mixed models or GEE, as appropriate.

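### Section 12.6 plans an all-grade adverse event summary, but 11.3 collects most terms only from grade 3, and 11.5 points to the wrong table for severity

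*Combined protocol and SAP*

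**What the plan says.** - **Recording rule (11.3).** "All AEs grade 3 or higher occurring during the reporting period must be assessed and recorded as follows". The exception, recorded from grade 1, is a short list: "Adverse events of special interest are: mucositis, infection, neutropenia, diarrhea, and thrombocytopenia". Section 11.7 adds that all serious adverse events are reported, with no grade limit.
- **Study calendar (Table 1, footnote c).** Adverse events are to be reported on the scheduled days, with no grade stated. Events between visits are captured if they meet criteria said to be in section 10. Section 10 contains no general recording threshold; the threshold is in 11.3.
- **Planned analysis (12.6).** "frequency and percentage of patients will be summarized for any adverse event by grade, attribution, organ class, and preferred term". Nothing limits this to grade 3 and above or to the special-interest terms.
- **Expected toxicity (10.1.1).** The most common treatment-related events among 648 patients with hematologic malignancies "include nausea (53.2%), diarrhea (47.7%), stomatitis (46.8%), febrile neutropenia (36.9%), decreased appetite (31.3%), vomiting (30.1%), anemia (29.0"%), followed by thrombocytopenia (28.5%), neutropenia (20.1%) and fatigue (21.0%). The same section adds: "The incidence of combined grade 3 and 4 nausea and vomiting in vosaroxin studies is low (2.7% and 1.4% respectively").
- **Severity where CTCAE has no criteria (11.5).** "it should be graded using the scale presented in Table 5". Table 5 is headed "Definition of Adverse Event Attribution" and runs from unrelated to definite.
- **Second induction (5.2.2).** "Eligibility for Induction 2 requires that non-hematologic toxicity and abnormal laboratory values be resolved to grade" 1 or lower, where the investigator judges them treatment-related and clinically significant.

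**The concern.** Safety and tolerability is the first-listed secondary objective, and 12.6 is where it is analyzed. The planned table covers all grades, while for most terms the data must be collected only from grade 3. A reader who sees nausea in about 1 of 41 patients in a table described as covering any adverse event could take that as an any-grade rate and set it against the 53.2% in 10.1.1. The apparent improvement would come from the collection rule.

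The error in 11.5 undermines the same rule from another side. An event without CTCAE criteria has no usable severity scale, so a site cannot decide whether it reaches grade 3 and must be recorded.

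Footnote c adds uncertainty. A site that follows it literally may record low-grade events on visit days, while a site that follows 11.3 need not. The grade 1-2 cells could then be filled unevenly across sites.

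**Working it through.** The plan states no figure for this gap, so there is none to reproduce. The size below uses the rates in 10.1.1 and the planned 41 patients.

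**Step 1. Which common terms are affected?** Section 10.1.1 lists ten terms at 20% or more.
- Recorded from grade 1 under 11.3: diarrhea, stomatitis (as mucositis), thrombocytopenia, neutropenia.
- Mostly grade 3-4 in any case: febrile neutropenia. Any-grade counts are 239 of 648 (36.9%) in hematologic patients and about 26 of 284 (9.2%) in solid-tumor patients. (239 + 26) / 932 = 28.4%, against 26.4% at grade 3-4 in the 932, a ratio of 28.4 / 26.4 = 1.08.
- Limited loss: anemia. The rate is 29.0% at any grade, against more than 20% at grade 3 or higher in the single-agent study in untreated AML (section 1.3), so the ratio is below 29.0 / 20 = 1.45. This is a cross-study comparison. Hemoglobin is also in the scheduled blood counts, and 12.6 grades laboratory data.
- Left exposed: nausea, vomiting, decreased appetite, fatigue.

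**Step 2. Expected counts in 41 patients, if the printed rates carry over.**

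| Term | Any grade | Grade 3-4 | Ratio of rates |
|---|---|---|---|
| Nausea | 41 × 0.532 = 21.8 | 41 × 0.027 = 1.1 | 53.2 / 2.7 = 19.7 |
| Vomiting | 41 × 0.301 = 12.3 | 41 × 0.014 = 0.6 | 30.1 / 1.4 = 21.5 |

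The chance that no patient has an event reaching the threshold is (1 − 0.027)^41 = 0.33 for nausea and (1 − 0.014)^41 = 0.56 for vomiting. For decreased appetite (31.3%) and fatigue (21.0%) the documents give no grade 3-4 rate, so no ratio can be computed.

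**Step 3. How firm are the ratios?** The any-grade rates are out of 648 hematologic patients. The grade 3-4 rates are given only for vosaroxin studies, without a denominator. No whole count out of 648 rounds to 2.7% (17 gives 2.6%, 18 gives 2.8%), but 25 of 932 does, and 932 = 648 + 284. Taking 932 as an assumption, 1.4% is 13 patients. The any-grade counts in the 932 are at least 345 (nausea) and 195 (vomiting), the hematologic counts, and at most those plus all 284 solid-tumor patients.
- Nausea: 345 / 25 = 13.8 to (345 + 284) / 25 = 25.2.
- Vomiting: 195 / 13 = 15.0 to (195 + 284) / 13 = 36.8.

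The ratios also assume that the grade 3-4 figures count treatment-related events, as the any-grade figures do; 10.1.1 does not say.

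**Step 4. Severity pointer.** No arithmetic applies. Section 11.5 asks for a severity grade from Table 5. Table 5 has five categories of causal relationship and none of intensity. No other fallback severity scale appears in the protocol.

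**The case against.** **A grade 3 threshold is not an error.** Recording grade 3 and above plus named special-interest events is a legitimate choice, and the grade 3+ rows of a by-grade table would be correct. This stands. The fault is that the analysis text does not carry the same limit; the table misleads only if it is read as an all-grade account, which is how 12.6 describes it.

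**Low-grade events may still reach the database.** Serious events are reported at any grade, footnote c sets no grade limit on visit days, and 11.3 states a minimum without forbidding more. This also stands, and it is why the rows should be called empty or incomplete. Uneven voluntary recording does not give a usable rate.

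**A reader might infer that the drug's commonest toxicities in general would be understated about 20-fold.** The documents do not support that. The factor can be computed only for nausea and vomiting, with unmatched denominators. The second and third commonest terms, diarrhea and stomatitis, are recorded from grade 1, and febrile neutropenia loses little.

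**A reader might also infer that the toxicity check before Induction 2 leaves no record.** That is too strong. The calendar schedules an adverse event evaluation and directed examination within 3 days of the second cycle's day 1, with a further evaluation and chemistry on day 1. Mucositis, diarrhea and infection are recorded from grade 1, and recorded events carry a stop date where available. The remaining gap is narrow: a grade 2 event that is non-serious, non-laboratory and outside the five terms need not be recorded, and for recorded events 11.3 asks for maximum grade, not the grade on that day.

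**Conclusion.** The point holds in limited form. Sections 11.3 and 12.6 do not match, and the Table 5 pointer in 11.5 is wrong on its face. Under the collection rule as written, about 1 of an expected 22 patients with nausea, and 0.6 of an expected 12 with vomiting, would have to be recorded. This assumes that the 10.1.1 rates apply to this trial's population, dose and schedule. If the grade 3-4 denominator is 932, the ratio is roughly 14 to 25 for nausea and 15 to 37 for vomiting. For decreased appetite and fatigue the direction is clear but the size cannot be derived.

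The number of events without CTCAE criteria is not given, so the reach of the Table 5 error cannot be sized; it is probably small. Both defects bear on the safety objective only. Sample size, type I error, power and the complete remission analysis are untouched. The correction should be made because the safety summary cannot be produced as described and the remedy costs almost nothing.

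**What to change.** 1. **Section 12.6:** limit the adverse event summaries to what 11.3 collects, and title the tables accordingly: *grade 3 or higher for all adverse events; all grades for special-interest adverse events only*. State how serious events below grade 3 are shown.
2. **Study calendar footnote c:** refer to 11.3 in place of section 10, and make clear whether the 11.3 threshold also applies on scheduled visit days.
3. **Section 11.5:** replace the pointer to Table 5 with an actual severity scale, leaving Table 5 for attribution.

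These are wording changes with no new data collection.

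Optional, at the cost of a few more CRF entries at visits already scheduled:
- Record nausea, vomiting, decreased appetite and fatigue at all grades, since 10.1.1 puts each above 20%. This is a choice about scope; items 1 to 3 are enough to remove the contradiction.
- At the adverse event evaluation within 3 days of the second cycle's day 1, note any ongoing treatment-related non-hematologic toxicity and its grade, so that the 5.2.2 check can be traced in the trial data. The Induction 2 rule itself is not changed.
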